16.6 Medical coding

Medical coding will be performed by trained personnel at CTC. AEs and medical/surgical history verbatim terms are coded using the medical dictionary of regulatory activities (MedDRA, latest version available at eCRF setup).

Prior and concomitant medications will be coded according to the World Health Organization (WHO) anatomic therapeutic chemical (ATC) classification system (latest version available at eCRF setup). All coding will be approved by the Sponsor prior to database lock.

16.7 Database lock

When all data has been entered and discrepancies solved, clean file will be declared, the database will be locked, and the data will be analyzed.

CONFIDENTIAL 65(76)

17 STATISTICAL METHODS AND DETERMINATION OF SAMPLE SIZE

The principal features of the statistical analysis to be performed are described in this section. A more technical and detailed elaboration of the principal features will be presented in a separate statistical analysis plan (SAP), which will be signed and approved prior to database lock.

17.1 General

Continuous data will be presented in terms of evaluable and missing observations, arithmetic mean, standard deviation (SD), median, minimum, and maximum value, Q1-Q3 (interquartile range [IQR]).

Categorical data will be presented as counts and percentages. When applicable, summary data will be presented by IP, and by assessment time. Individual subject data will be listed by subject number, IP, and, where applicable, by assessment time.

All descriptive summaries and statistical analyses will be performed using SAS Version 9.4 or later (SAS Institute, Inc., Cary, NC, US). The PK parameters will be calculated by non-compartmental analysis using the software Phoenix WinNonlin® version 8.3 or later (Certara Inc., Princeton, NJ, US).

For Part 2, baseline will be defined as the last data collection point prior to each IP use.

No adjustment for multiple comparisons will be performed. All formal comparisons will be made toward a designated reference product and all significant findings will be reviewed for medical relevance.

17.1.1 Missing, unused and spurious data

Generally, no imputation of data will be performed. In case of missing start and stop times of AEs that cannot be investigated further, missing data will be imputed according to a worst-case scenario, *i.e.*, start time will be imputed as the closest time point post intake of IP and end time as 23:59, resulting in the longest possible treatment emergent duration of the AE.

Spurious data will be evaluated continuously through data validation (see Section 16) and, if connected to protocol deviations, evaluated case-by-case at the latest prior to declaration of clean file and database lock.

Deviations from the original SAP will be described in the CSR.

Methods for handling of missing, unused, and spurious data will be further specified in the SAP.

[figure not shown]
17.2 Determination of sample size

The study will include approximately 53 subjects with the aim of randomizing at least 53 subjects in Part 2 and achieving 45 evaluable subjects (for Part 2).

The sample size has been calculated considering the primary endpoint: to compare the exposure in terms of AUC_{inf} between the NP 11 mg and the comparator, Swedish snus 18 mg. Using a coefficient of variation (CV) of 33 %, based on previous studies, a power of 90%, a significance level of 5% (as judged by a 95% confidence interval) and an upper non-inferiority bound for the back-transformed geometric means ratio of 1.25 (NP 11 mg/comparator), 45 evaluable subjects will be needed. Assuming a dropout rate of 15%, a total of 53 subjects will be randomized.

Refer to Section 17.6.1 for a full description of the envisioned primary analysis model.

CONFIDENTIAL 66(76)

Efforts will be made to include at least 21 female subjects (approximately 40%). However, a minimum of 11 female subjects (approximately 20%) will be considered acceptable. Additionally, efforts will be made to include 10 to 15 regular users of loose snus. These subjects will use a loose snus of their choice as their own brand product during both Part 1 and Part 2.

17.3 Analysis data sets

17.3.1 Full analysis set

The Full analysis set (FAS) will consist of all subjects who have been randomized and used at least 1 IP. This population will be used for the safety analysis set.

17.3.2 PK analysis set (Part 2 only)

The PK analysis set (PKAS) will consist of all subjects who used at least 1 IP and provided at least 1 evaluable PK profile, and no major deviation or AEs judged to compromise the PK analysis. Individual PK values and/or full profiles for explicit IPs may be excluded from the analysis as specified in the SAP.

17.4 Pharmacokinetic analysis - general

The PK analysis will be based on the PKAS and performed by CTC. The PK parameters will be calculated by non-compartmental PK analysis using the software Phoenix WinNonlin® version 8.3 or later (Certara Inc., Princeton, NJ, US). In addition to AUC_{0-inf} and C_{max} parameters, other non-compartmental PK parameters will be determined in relation to secondary endpoints (see Section 17.7.1 below). Where possible, both baseline-adjusted and non-adjusted PK parameters will be calculated.

For AUC_{0-inf} , the area under the plasma concentration vs. time curve will be calculated to the time point of the last quantifiable plasma concentration of nicotine and then extrapolated to infinity using the concentration in the last quantifiable sample and the estimated terminal elimination rate constant (Lambda_z).

PK data will be presented for each IP using summary statistics. This data will be presented in terms of N, arithmetic mean, median, SD, minimum and maximum value. For applicable PK parameters, the geometric mean and CV % will be presented. Categorical data will be presented as counts and percentages, as applicable.

17.5 Description of study population

17.5.1 Demographics and baseline characteristics

Descriptive statistics for demographics, weight, height, BMI, history of oral tobacco/nicotine use, Fagerström nicotine dependency test scores, and smoking will be presented for all subjects. All data will be listed by subject number.

17.5.2 Medical/surgical history and prior/concomitant medication

Medical/surgical history will be presented by system organ class (SOC) and preferred term (PT). Prior/concomitant medications will be presented by ATC level 4 and 5. All data will be listed by subject number.

CONFIDENTIAL 67(76)

17.5.3 Investigational product use

The number of subjects who used each IP will be presented through listings. Subject's own brand will be listed.

17.5.4 Physical examination

Physical examination parameters will be specified as "normal", "abnormal, not clinically significant", or "abnormal, clinically significant (as judged by the Investigator at the screening visit) and summarized.

All data will be listed by subject number.

17.5.5 Vital signs

Vital signs (systolic/diastolic blood pressure, and pulse rate) will be summarized by IP. All data will be listed by subject number.

17.5.6 Electrocardiogram

All ECGs will be categorized as" normal"," abnormal, not clinically significant", or" abnormal, clinically significant" (as judged by the Investigator at the screening visit) and summarized.

All data will be listed by subject number.

17.6 Analysis of primary endpoint

17.6.1 Comparison of the NP 11 mg and Swedish snus comparator (AUC_{0-inf})

The primary endpoint of this study is to compare nicotine exposure, as measured by baseline-adjusted AUC_{0-inf} based on nicotine plasma concentrations, between the NP 11 mg product and the comparator product, Swedish snus pouch 18 mg. The goal is to demonstrate that the upper bound of the 95 % confidence interval of the ratio for nicotine exposure of the moist NP 11 mg product and the comparator Swedish snus product is at or below 1.25.

AUC_{0-inf} will be calculated as described in Section 17.4 above.

The comparison of AUC_{0-inf} between the NP 11 mg and the comparator Swedish snus pouch 18 mg will be assessed using the following null (H_0) and alternative (H_1) hypotheses:

$$H_0: \frac{\mu_T}{\mu_R} > 1.25$$

$$H_1: \frac{\mu_T}{\mu_R} \le 1.25$$

where μ_T is the least-squares geometric mean of $AUC_{0\text{-inf}}$ for the NP 11 mg and where μ_R is the least-squares geometric mean of $AUC_{0\text{-inf}}$ for the comparator Swedish snus pouch 18 mg.

In the analysis, a mixed model will be used with the natural log of $AUC_{0\text{-inf}}$ as the dependent variable, treatment as a fixed effect and subject as a random effect. The improved Kenward-Roger's approximation for degrees of freedom [23] will be used. The estimated least-squares means difference between the NP 11 mg and the comparator Swedish snus pouch 18 mg will be back-transformed into the original scale to present the ratio of geometric least square means as well as the corresponding 95 % confidence interval. If the upper bound of the interval of this ratio is at or below 1.25, the null hypothesis will be rejected, and it will be concluded that the NP 11 mg product does not result in substantially higher nicotine exposure compared to the comparator product.

CONFIDENTIAL 68(76)

17.7 Analysis of secondary endpoints

17.7.1 In vivo extracted amount and fraction of nicotine (Part 2 only)

The difference between the nicotine content of an unused reference pouch or loose snus portion and the used study pouch/portion will be used to calculate the *in vivo* extracted amount and fraction of nicotine for each IP. Extracted amount and fraction of nicotine will be presented using summary statistics. The amount of nicotine in the reference pouches or loose snus portions and in used pouches or loose snus portions will be presented through descriptive statistics.

In addition, extracted amount and fraction of nicotine will be analyzed exploratively using the same model as described in Section 17.6.1 to quantify estimated differences between products.

17.7.2 Pharmacokinetics of nicotine in plasma (Part 2 only)

The following non-compartmental PK parameters will be determined for each IP: AUC_{0-inf} , AUC_{0-last} , $AUC_{0-l.5h}$, C_{max} , T_{max} , and $T_{1/2}$. Where possible, both baseline-adjusted and non-adjusted PK parameters will be calculated.

 C_{max} and T_{max} will be derived from the observed nicotine plasma concentration data. AUC_{0-1.5h}, AUC_{0-last}, and AUC_{0-inf} will be calculated using log-linear trapezoidal interpolation. Calculations will be based on the actual sampling times recorded during the study. Concentrations below the lower limit of quantification (LLOQ) occurring before C_{max} will be treated as zero. Concentrations below LLOQ occurring after C_{max} will be omitted from the analysis. All baseline-adjusted PK parameters will be corrected for nicotine plasma concentrations at baseline (pre-use).

AUC_{0-inf} will be calculated as described in Section 17.4 above.

The continuous secondary PK parameters (i.e., all of the above except T_{max}) will be analyzed for both non-baseline-adjusted, and baseline-adjusted concentrations using the same model as described in Section 17.6.1 to assess non-inferiority between each test product and each comparator product respectively.

In addition, descriptive statistics for secondary PK parameters and concentrations (baseline-adjusted and non-baseline-adjusted) will be presented. PK plasma concentration curves over time will be presented.

All data will be listed by subject number.

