7.2 Secondary objectives and endpoints

The secondary study objectives and endpoints are presented in Table 7.2-1.

Table 7.2-1 Secondary study objective and endpoint

No.	Secondary objectives	No.	Endpoints	Assessments	Analysis
1.	To compare the in vivo extracted amount (mg/unit) and extracted fraction (%) of nicotine between the moist NP 6 mg, 11 mg, and 16.6 mg products and the comparator products, Swedish snus 18 mg and own brand snus product.	1.	The difference in in vivo extracted amount (mg/unit) and extracted fraction (%) of nicotine between the moist NP 6 mg, 11 mg, and 16.6 mg products and the comparator products, Swedish snus 18 mg and own brand snus product.	(Section 11.5.2)	See Section 17.7.1.
2.	To compare the pharmacokinetic (PK) profile between the moist NP 6 mg, 11 mg, and 16.6 mg products and the comparator products, Swedish snus 18 mg and own brand snus product.	2a.	The difference between the moist NP 6 mg, 11 mg, and 16.6 mg products and the comparator products, Swedish snus 18 mg and own brand snus product, in the non-adjusted and baseline-adjusted PK parameters based on plasma concentrations of nicotine: $AUC_{0\text{-inf}}, \text{ maximum observed plasma concentration } (C_{\text{max}}), \text{ time to } C_{\text{max}} (T_{\text{max}}), AUC \text{ from 0 to 1.5 hours } (AUC_{0\text{-1.5h}}), AUC \text{ from 0 to time of last measurable time point } (AUC_{0\text{-last}}), \text{ and terminal elimination half-life } (T_{1/2}).$	(Section 11.5.1)	See Section 17.7.2.
		2b.	To compare nicotine exposure, as measured by non-adjusted and baseline-adjusted AUC _{0-inf} , between the moist NP 6 mg and NP 16.6 mg products and the	(Section 11.5.1)	See Section 17.7.2.

CONFIDENTIAL 26(76)

			comparator products, Swedish snus 18 mg and own brand snus product. This comparison also includes the NP 11 mg product and the own brand snus product. (The goal is to demonstrate that the upper bound of the 95% confidence interval for the ratio for nicotine exposure between the moist NP products and the comparator products is at or below 1.25.)		

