10.5 Investigational product use instructions

In Part 1 and Part 3, the subjects will use their own brand snus product (Part 1) or the selected NP (Part 3) *ad libitum* throughout the 14-day period.

In Part 2, a single dose will be given in the morning of each IP use visit (Visits 4-8). Subjects will keep the pouch/portion between their upper lip and gum for 30 minutes and will be

CONFIDENTIAL 42(76)

instructed not to eat or drink, chew gum, or brush their teeth for 30 minutes before, during use, and 30 minutes after the use of IP.

Subjects shall abstain from oral tobacco/nicotine products as well as smoking (cigarettes or ecigarettes) for at least 12 hours prior to each IP use visit. To this end, subjects will be instructed to abstain from such products from approximately 20:00 (8 pm) the day before IP use visits (Visits 4-8). All IP uses will be performed during the morning hours (08:00 to 12:00) to facilitate abstinence.

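### Endpoint 2b also applies the 1.25 rule to non-adjusted AUC0-inf, where leftover nicotine pulls a ratio above 1 towards 1, and the protocol does not say which scale decides

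*Protocol*

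**What the plan says.** The primary endpoint (protocol Sections 7.1 and 17.6.1) compares NP 11 mg with the 18 mg snus on baseline-adjusted AUC0-inf only, with success if the upper 95% limit of the ratio is at or below 1.25.

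Secondary endpoint 2b (Section 7.2, Table 7.2-1) covers the remaining pairs of pouch and comparator, including own brand snus. It measures exposure by non-adjusted and baseline-adjusted AUC0-inf and carries the same criterion over: "The goal is to demonstrate that the upper bound of the 95% confidence interval for the ratio for nicotine exposure between the moist NP products", set against their comparators, does not exceed 1.25. Section 17.7.2 confirms that the continuous PK parameters are modelled "for both non-baseline-adjusted, and baseline-adjusted concentrations using the same model as described in Section 17.6.1 to assess non-inferiority between each test product", taken against every comparator in turn. The pre-use correction applies only to the baseline-adjusted parameters.

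For Part 2, "subjects will be instructed to abstain from such products from approximately 20:00 (8 pm) the day before IP use visits" (Section 10.5), and products are used between 08:00 and 12:00. The abstinence is therefore 12 to 16 hours in people who use at least five portions a day (Section 9.4). Section 17.1 makes no multiplicity adjustment. The protocol gives no expected pre-use nicotine level.

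**The concern.** Section 6.2 says that Part 2 is meant to assess product-specific nicotine exposure, and Section 8.2 gives avoidance of carry-over as the reason for the abstinence. On the non-adjusted scale the quantity tested is not the product ratio A_T/A_R but (A_T+B)/(A_R+B), where A is the AUC due to the product (T test, R comparator) and B is the AUC of nicotine already in the body. Whenever A_T/A_R exceeds 1 and B is positive, the second ratio is nearer to 1. For a rule meant to exclude an exposure more than 25% higher, that error favours the claim.

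The same pair of products can also fail on the adjusted scale and pass on the non-adjusted one, and nothing says how endpoint 2b is then read. Section 6.3.3 says the results can guide nicotine limits, so a favourable verdict should not come partly from snus used the evening before.

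**Working it through.** **Inputs (Section 17.2).**
- Variability: "Using a coefficient of variation (CV) of 33 %, based on previous studies". I take this CV as within-subject.
- Error level: "a significance level of 5% (as judged by a 95% confidence interval").
- Power: 90%.
- Margin on the ratio scale: "an upper non-inferiority bound for the back-transformed geometric means ratio of 1.25 (NP 11 mg/comparator").
- Planned evaluable number: 45 subjects.
- Allowance for loss: "Assuming a dropout rate of 15%, a total of 53 subjects will be randomized".

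**Step 1: reproduce the plan's sample size.**
- Log-scale SD = √ln(1+0.33²) = 0.3215. SD of a paired difference = 0.3215×√2 = 0.4547. Margin = ln 1.25 = 0.2231.
- With one-sided 2.5% and a true ratio of 1 (not stated in the protocol), the normal approximation is n = (1.960+1.282)²×0.4547²/0.2231² ≈ 43.6, so 44.
- With the noncentral t distribution, n = 46 on n−1 degrees of freedom (power at 45 is 89.6%), or 45 on 4(n−1) from the five-product model (power at 45 is 90.6%).
- One-sided 5% would need only 36 or 37. So 45 is reproduced, and the error rate in use is one-sided 2.5%.
- 45/0.85 = 52.9, so 53 randomized.

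**Step 2: expected non-adjusted ratio.** Let b = B/A_R (an assumption, since the protocol gives no value) and let R be the true product ratio. The expected non-adjusted ratio is (R+b)/(1+b). At R = 1.25 and b = 0.10 this is 1.35/1.10 = 1.227. At b = 0.20 it is 1.45/1.20 = 1.208.

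**Step 3: pass rate at R = 1.25.** With 45 subjects the standard error is 0.4547/√45 = 0.0678. The probability that the upper 95% limit is at or below ln 1.25 comes from the noncentral t with 44 degrees of freedom and noncentrality [ln 1.25 − ln((1.25+b)/(1+b))]/0.0678. A simulation of 40,000 trials also lets the added residual shrink the log-scale SD. It assumes a between-subject log SD of 0.3 or 0.5 and a residual CV of 60% between and 40% within subjects.

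| b (assumed) | Expected non-adjusted ratio | Pass rate, closed form | Pass rate, simulated |
|---|---|---|---|
| 0 | 1.250 | 2.5% | 2.5% |
| 2% | 1.245 | 2.9% | 3.0% |
| 5% | 1.238 | 3.4% | 3.8–4.0% |
| 10% | 1.227 | 4.5% | 5.6% |
| 20% | 1.208 | 7.1% | 9.8–10.2% |
| 30% | 1.192 | 10.1% | 14.9–15.5% |

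In the same simulations the baseline-adjusted test passes 2.3–2.6% of the time at every b. If either scale may support the claim, the rate is essentially the non-adjusted one. If both must pass, it is again 2.3–2.5%.

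**Step 4: where the excess stops.** Setting (R+b)/(1+b) = 1.25 gives R = 1.25+0.25b: 1.275 at b = 10% and 1.30 at b = 20%. Above that the closed-form pass rate is below 2.5%. For example, R = 1.35 with b = 20% passes 0.75% of the time.

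**The case against.** The primary conclusion rests on baseline-adjusted AUC0-inf alone, and every secondary pair is also tested on that scale, so no adjusted result is hidden. That stands, and it limits the point to endpoint 2b.

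The non-adjusted test keeps its size for its own hypothesis, total plasma exposure. That is also true. The excess appears only when the result is read as a statement about the product, but product-specific exposure is what Section 6.2 says Part 2 is for.

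Endpoint 2b joins the two scales with "and", so both might be required, and then there is no excess. The protocol does not state that reading, nor that either scale suffices. This is the gap to close.

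The size rests on an assumed b. If pre-use samples fall below the quantification limit they count as zero under Section 17.7.2, and there may be little or no effect.

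A reader might infer that any pouch above the margin is passed too often. Step 4 shows otherwise: the excess lies in a narrow band. As a rough guide, the one-hour extraction figures in Section 6.1 (39% for pouches, 24% for loose snus), applied to nominal contents, give ratios to the 18 mg snus of 2.34/4.32 = 0.54, 4.29/4.32 = 0.99 and 6.47/4.32 = 1.50, none of them in the band. Own brand ratios are unknown. If one assumes a 1 g portion at the 8–10 mg/g in Section 6.1, NP 6 mg gives 2.34/2.40 to 2.34/1.92, or 0.98 to 1.22, so the margin region is not remote. Part 2 use lasts 30 minutes, so both sets are illustrative only. For ratios below 1 the pull works against the claim.

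A reader might also infer that a stated error rate is broken throughout. Section 17.2 states 5% for the primary comparison only. Measured against a literal 5%, the rate is exceeded only somewhere between b = 10% and 15% in closed form, or between 5% and 10% in simulation.

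**Conclusion.** The point holds for secondary endpoint 2b. Applying the 1.25 rule to non-adjusted AUC0-inf biases a product ratio above 1 in the favourable direction whenever residual nicotine is present, and the protocol leaves open which scale decides. At a true product ratio of 1.25 the rule passes 2.5% of the time with no residual, about 3% at a 2% share, 3.4–4.0% at 5%, 4.5–5.6% at 10%, 7–10% at 20% and 10–15% at 30%.

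These figures assume 45 evaluable subjects, a within-subject CV of 33% and a residual equal for both products in expectation (same abstinence rule, randomized order), though not at each visit. The documents do not say where in this range the trial would fall, so no single inflated rate can be claimed. The direction is certain, the size is not, and the missing decision rule matters whatever the size.

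**What to change.** In endpoint 2b (Table 7.2-1 and the synopsis) and in Section 17.7.2, state that baseline-adjusted AUC0-inf alone decides every 1.25 conclusion, as it already does for the primary endpoint. Report the non-adjusted ratio with its 95% confidence interval as supportive, without a non-inferiority verdict of its own. Requiring both scales to pass would also restore about 2.5%, if the sponsor prefers to keep a formal test on each.

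The change is to wording only and needs no extra data or subjects. The cost is fewer formal claims on the secondary comparisons.

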8 STUDY DESIGN

8.1 Overall study design and schedule of events

This is a multi-center, open-label, three-part study:

- Part 1: a multi-center, non-randomized observational part involving use of the subject's own brand Swedish snus product of choice (hereafter, called own brand snus) *ad libitum* (see Section 8.1.1).
- Part 2: an open-label, multi-center, randomized, 5-way cross-over, single use part. The investigational products (IPs) include three moist NP products, containing 6 mg/unit, 11 mg/unit, and 16.6 mg/unit of nicotine. The comparator products include one Swedish snus 18 mg/unit product and subject's own brand snus product (see Section 8.1.2).
- Part 3: a multi-center, non-randomized interventional part involving complete substitution of own brand snus product with a NP product for *ad libitum* use (see Section 8.1.3).

[figure not shown]
The study will include approximately 53 subjects with the aim of randomizing at least 53 subjects in Part 2 and achieving 45 evaluable subjects (for Part 2).

The subjects will be healthy male and female subjects who have used Swedish snus products for ≥1 year, with a minimum daily consumption of 5 pouches/portions. Efforts will be made to include at least 21 female subjects (approximately 40%) in Part 2. However, a minimum of 11 female subjects (approximately 20%) will be considered acceptable. Additionally, efforts will be made to include 10 to 15 users of loose snus.

Each subject will participate in the study for approximately 7 weeks, not including the preceding up to 5-week screening period.

An overview of the study design is shown in Figure 8.1-1. An overall schedule of event is presented in Table 8.1-1 and a detailed schedule of events for each IP use visit in Part 2 is presented in Table 8.1-2. Study assessments are described in Section 11.

Figure 8.1-1 Overview of the study design

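### Section 17.7.2 assesses non-inferiority for every continuous PK parameter, half-life included, although Table 7.2-1 sets that goal for AUC0-inf only

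*Protocol*

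**What the plan says.** Section 17.7.2 of the protocol lists six PK parameters: AUC0-inf, AUC0-last, AUC0-1.5h, Cmax, Tmax and T1/2. It then says: "The continuous secondary PK parameters (i.e., all of the above except" Tmax) "will be analyzed for both non-baseline-adjusted, and baseline-adjusted concentrations", using the model of Section 17.6.1, "to assess non-inferiority between each test product and each comparator product respectively". Only Tmax is left out, so T1/2 is in. Descriptive statistics are given in addition.

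Table 7.2-1 in Section 7.2 has two endpoints for the same objective, and both point to Section 17.7.2:

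- Endpoint 2a is the difference between products "in the non-adjusted and baseline-adjusted PK parameters based on plasma concentrations of nicotine". It covers all six parameters and names no goal and no bound.
- Endpoint 2b begins "To compare nicotine exposure, as measured by non-adjusted and baseline-adjusted AUC"0-inf. It alone carries the goal that the upper 95% confidence bound of the ratio does not exceed 1.25. It names its pairs: NP 6 mg and NP 16.6 mg against both comparators, and NP 11 mg against own brand.

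For exposure in Part 2, the 1.25 bound otherwise appears only for the primary AUC0-inf comparison (Table 7.1-1, Sections 17.2 and 17.6.1).

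**The concern.** The analysis section goes further than the endpoints it implements. Endpoint 2a asks how far the products differ. Section 17.7.2 turns that into a question of non-inferiority, for parameters to which no endpoint attaches such a goal. A statistician who follows 17.7.2 and one who follows Table 7.2-1 would report different sets of conclusions from the same models.

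The mismatch matters most for T1/2. The conclusion built into Section 17.6.1 is about nicotine exposure, and half-life does not measure exposure. A statement that a pouch is non-inferior on half-life could stand in the report beside the AUC0-inf statements and look like further evidence on the same question. Section 6.3.3 says the results may guide recommendations on nicotine limits, so it should be clear which conclusions were planned as goals.

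**Working it through.** **The plan's own figure.** The protocol gives no count of secondary comparisons. The related figure is the sample size in Section 17.2, which shows what the 1.25 bound was set up for. Inputs: CV 33%, power 90%, a 95% confidence interval of which only the upper bound is used (one-sided 2.5%), bound 1.25. The true ratio is not stated; 1.0 is assumed here.

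- Within-subject SD on the log scale: √ln(1 + 0.33²) = 0.3215. Log bound: ln 1.25 = 0.2231.
- Normal approximation: n = 2 × [0.3215 × (1.960 + 1.282) / 0.2231]² ≈ 43.6, so 44.
- Non-central t: 45 with 4(n − 1) degrees of freedom (power 0.906 at 45), or 46 with n − 1 (power 0.896 at 45).
- Dropout: 45 / 0.85 = 52.9, so 53.

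The stated 45 and 53 are reproduced. The calculation concerns AUC0-inf only.

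**Comparisons covered by Section 17.7.2.** There are 5 parameters (six listed, less Tmax) and 2 versions (adjusted and non-adjusted). There are 3 test products, at 6, 11 and 16.6 mg, and 2 comparators (Section 8.1: "The comparator products include one Swedish snus 18 mg/unit product and subject's own brand snus product").

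- 5 × 2 × 3 × 2 = 60. Less the primary comparison (baseline-adjusted AUC0-inf, NP 11 mg against snus 18 mg), 59 remain.

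**Comparisons called for by endpoint 2b.** Pairs: 2 × 2 + 1 = 5. Versions: 2.

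- 5 × 2 = 10.

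**The difference.** 59 − 10 = 49, made up as follows:

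- AUC0-last, AUC0-1.5h and Cmax: 3 × 2 × 6 = 36.
- T1/2: 1 × 2 × 6 = 12.
- Non-adjusted AUC0-inf for NP 11 mg against snus 18 mg, a pair that endpoint 2b does not list: 1.

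**Why T1/2 stands apart.** With linear elimination (an assumption), AUC0-inf = amount absorbed / clearance, while T1/2 = ln 2 × volume / clearance. The amount absorbed enters the first and not the second. In Part 2 the pouch is removed after 30 minutes and sampling runs to 6 hours (Section 8.1.2), so the terminal phase comes after delivery has ended. In a cross-over each subject brings the same clearance to every product, so the ratio is expected near 1 whatever the nicotine content. An upper bound below 1.25 on that ratio therefore does not bear on exposure.

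**Wording next door.** Section 17.7.1 uses the same model for extracted nicotine in an exploratory way, to estimate differences between products, with no non-inferiority. That is the form that endpoint 2a needs.

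**The case against.** The best case for the plan is that Section 17.7.2 borrows a model and a purpose but does not restate the 1.25 bound, a null hypothesis or a decision rule for the other parameters. The model still delivers the ratio and its interval, which answers endpoint 2a, and descriptive statistics are given as well. How secondary results are worded could be left to the SAP. In addition, an upper-bound question suits most of these parameters: Section 6.1 links a higher Cmax to addiction potential, Section 6.2 wants pouches not to exceed snus in that respect, and the partial AUCs are measures of exposure.

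Much of this stands. No estimate or interval is wrong, and a non-inferiority reading of Cmax, AUC0-last or AUC0-1.5h is not meaningless; it merely lacks a stated goal and bound. What the objection does not remove is that the protocol itself prescribes non-inferiority here. That is a stated rule at odds with Table 7.2-1, not a detail left open, and an SAP written to 17.7.2 would inherit the conflict. Nor does it rescue T1/2.

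A reader might go further and infer a multiplicity failure, reckoning 59 × 0.025 ≈ 1.5 false non-inferiority claims. The document does not support this. The figure needs every true ratio to sit exactly at 1.25, including NP 6 mg against an 18 mg snus, and it counts 12 half-life comparisons whose true ratio is expected near 1 and which cannot then yield false claims. The protocol also says openly, "No adjustment for multiple comparisons will be performed", with a single primary comparison; for secondary endpoints that is a declared choice and not an error.

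**Conclusion.** The point holds as a mismatch of scope. Section 17.7.2 assesses non-inferiority for five parameters, whereas Table 7.2-1 sets that goal for one. Of the 59 comparisons besides the primary, 10 are called for by endpoint 2b and 49 are not. For the 12 on T1/2, the conclusion would say nothing about nicotine exposure from the product.

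The counts assume that each test product against each comparator means all six pairs, and that the last sentence on pairs in endpoint 2b means NP 11 mg against own brand. The T1/2 argument assumes elimination that does not depend on the product.

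A reader might also infer that the extra statements overstate the case for the products or weaken the primary result. Nothing in the protocol counts secondary verdicts as support for the primary conclusion, and the primary analysis and its sample size are untouched. The matter is minor: the wording of an analysis section needs to match its endpoints.

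**What to change.** Rewrite the sentence in Section 17.7.2 so that:

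- non-inferiority, with the upper 95% bound at or below 1.25, is assessed for AUC0-inf only, for the pairs and versions named in endpoint 2b;
- AUC0-last, AUC0-1.5h and Cmax, and any AUC0-inf comparison outside endpoint 2b and the primary, are reported as geometric mean ratios with 95% confidence intervals and no verdict, as endpoint 2a asks;
- T1/2 is reported without a non-inferiority conclusion.

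If the sponsor wants an upper-bound conclusion for Cmax because of the addiction-potential question, Cmax should be added to endpoint 2b with its bound stated.

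The cost is one sentence in a protocol amendment, and the SAP should follow it. The same models are run on the same data. The downside is fewer non-inferiority statements in the report.
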